8.1. Primary Efficacy Analysis

Not applicable.

8.2. Secondary Efficacy Analysis

8.2.1. Investigator Global Assessment (IGA)

The IGA is an ordinal scale with five severity grades which is reported only in integers.

[Table 4](#) illustrates the description of each severity grade.

Table 4: IGA

Score	Description
0	Completely clear: No erythema, no scaling (hypo-hyperpigmentation can be present)
1	Almost clear: Residual slight erythema and/or trace amounts of scaling
2	Mild: Pink to red color and/or slight scaling
3	Moderate: Distinct redness and/or clearly visible scaling
4	Severe: Severe erythema (intense, fiery red) and/or severe scaling (coarse, thick scales with flaking onto clothes or skin)

IGA grade

IGA grade and change from baseline will be summarized using descriptive statistics at each visit by groups and overall.

The number and percentage of subjects in each IGA grade category will be summarized by cohort, group, and overall.

The number and percentage of subjects who achieve IGA 0 or 1 will be tabulated at each scheduled visit by groups and overall. In addition, the achievement of IGA of 0, the achievement of IGA success (i.e., IGA of 0 or 1 plus a 2-grade improvement from Baseline) also will be tabulated. Furthermore, 95% CIs for proportion of subjects who meet the criteria will be provided along with proportions. IGA success from OLE baseline should exclude subjects who already achieved IGA of 0 or 1 at OLE baseline.

IGA success, IGA of 0 or 1, IGA of 0 at any time post baseline including the assessments at the unscheduled visit will be summarized by groups and overall, along with 95% CIs for proportion of people who meet the criteria.

These analyses are repeated for both primary and OLE baselines. The subjects who achieved IGA of 0 or 1 at baseline will be excluded from the analysis of IGA success from baseline.

Subgroup analyses will be performed for both primary and OLE baseline for the subgroups mentioned in Section [6.1.6](#).

Duration of IGA success, Duration of IGA of 0 or 1, and Duration of IGA of 0

This analysis will be performed using IGA grade assessed in the open-label study.

Duration of IGA success, for subjects whose IGA grade is not 0 or 1 at OLE baseline, is defined as the time from the first observation of IGA success to first subsequent time a subject's disease response does not meet the criteria for IGA Success. The duration of IGA success for subjects who end treatment in IGA success will be censored at the last disease assessment date. Only the first IGA success duration will be analyzed.

If there is no IGA assessment after the first observation of IGA success, the duration will be censored at the end of study date.

The median time (number of days) for IGA success will be analyzed using the Kaplan–Meier method. Subjects who discontinue study without relapse will be considered censored in the Kaplan–Meier analyses. The Kaplan–Meier estimate will be stratified by the IGA success time (IGA success by Week 4, between Week 4 and Week 12, between Week 12 and Week 24, between Week 24 and Week 36, and between Week 36 and Week 52).

Duration of IGA success will be summarized by Cohort, Groups, and overall.

The analysis of duration of IGA of 0 or 1 will be performed in the similar fashion.

Duration of IGA of 0 will be performed for subjects who achieve IGA of 0 post OLE baseline and stop treatment. Subjects who achieve IGA of 0 but never stop treatment will be excluded from analysis. If subject achieved IGA of 0 but stop treatment several days later, the duration

will start at the IP stop date. The analysis of duration of IGA of 0 will be in the similar fashion as the analysis for duration of IGA success.

Similar analysis from primary baseline will be performed.

Disease recurrence

This analysis will be performed using IGA assessments during the open-label study.

Time to disease recurrence is defined as time from first observation of IGA of 0 and stop treatment to first observation of IGA of 2 or higher after stop treatment. Subjects who achieve IGA of 0 but never stop treatment will be excluded from analysis. If subject achieve IGA of 0 but stop treatment several days later, the duration will start at the IP stop date. If there is other IGA assessment after achieving IGA of 0, the time to disease recurrence will be censored at the last disease assessment date. If there is no IGA assessment after the first observation of IGA success, the duration will be censored at the end of study date. The analysis of time to disease recurrence will be in the similar fashion as the analysis of duration of IGA success.

Similar analysis from primary baseline will be performed.

Treatment Free Interval

Time to restarting study drug (treatment free interval), defined as time from when subject achieves disease clearance (IGA of 0) and stop treatment to all lesions to time when treatment restarts due to IGA of 2 or above, will be calculated and summarized in the same manner as duration of IGA success. The number (%) of subjects who achieved disease clearance (IGA of 0) and stopped treatment will be presented as well. If the subjects never restart the study treatment after achieving IGA of 0, the subject will be censored at the end of study date.

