4.2.2. Secondary Endpoints

The secondary endpoints are related to efficacy and will include:

- Achievement of an Investigator Global Assessment (IGA) of 'completely clear' or 'almost clear', as observed over time
- A 2-grade improvement in IGA from Baseline (see [Section 7.1.1](#)) as observed over time
- 'IGA Success', defined as achievement of an IGA of 'completely clear' or 'almost clear' plus a 2-grade improvement in IGA from Baseline (see [Section 7.1.1](#)) as observed over time
- Duration of IGA Success, defined as the time from the first observation of IGA Success to the last time a subject's disease response meets the criteria for IGA Success. The duration of IGA Success for subjects who end treatment in IGA Success will be censored at the last disease assessment date
- Treatment-free interval, defined among subjects who achieve a 'completely clear' IGA and stop treatment to all lesions, as the time from attainment of a score of 'completely clear' to re-starting investigational product.

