6.5. Unscheduled Visit

Subjects that clear between scheduled visits should return for an unscheduled visit for the Investigator to confirm IGA score are considered 'clear' and subject will stop application of investigational product after Investigator confirmation. Subjects will call the site when seborrheic dermatitis returns prior to restarting application of investigational product. Unscheduled visits may also be necessary to repeat testing following abnormal laboratory

results, for follow-up of AEs, or for any other reason, as warranted in the judgment of the Investigator.

The following information will be collected for all subjects:

- AEs
- Concomitant medications/procedures

The following information will be collected for those subjects that had stopped study medication but are experiencing a reoccurrence of seborrheic dermatitis. These subjects may have an unscheduled visit (although an unscheduled visit is not required as subjects only need to call the site) when seborrheic dermatitis returns prior to restarting application of investigational product:

- IGA

An updated Body Diagram of seborrheic dermatitis involvement should be provided to the subject.

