6.1.7. Derived Variables

- **IGA success** = IGA of “completely clear” or “almost clear” plus a 2-grade improvement from Baseline. For IGA success analysis, the subjects who achieved IGA of 0 or 1 at baseline will be excluded from the analysis.
- **Erythema success** = Erythema score of 0 or 1 plus a 2-grade improvement from Baseline as observed over time. For erythema success analysis, the subjects who achieved erythema score of 0 or 1 at baseline will be excluded from the analysis.
- **Scaling success** = Scaling score of 0 or 1 plus a 2-grade improvement from Baseline as observed over time. For scaling success analysis, the subjects who achieved scaling score of 0 or 1 at baseline will be excluded from the analysis.
- **Compliance** = number of applications divided by the expected number of investigational product (IP) applications for each subject. Compliance will be calculated using drug accountability data over the entire treatment period for each subject, up to treatment completion or discontinuation.
- **Number of expected IP applications** = calculated as last treatment date - first treatment date + 1. Excluding treatment-free interval time (defined in this section).
- **Number of IP applications** = number of expected IP applications – missed IP applications as collected in the CRF. Missed IP applications will not be taken into consideration in determining number of IP applications if the reason for missing dose is per investigator confirmation of clear.

- **Days on IP** = last date of IP application – first date of IP application +1. Subjects that stop taking IP per investigator confirmation of clear will be excluded from this calculation.
- **Treatment Gap** = This will be calculated for subjects belonging to Cohort 2 Group 3 that rolled into the extension study (ARQ-154-214) with a gap. This is derived start treatment start date in ARQ-154-214 – last treatment date in ARQ-154-203 + 1.
- **Treatment Duration (weeks)** = (last date of IP application – first date of IP application +1)/7.
- **Duration of IGA success** = The date of first observation where IGA does not meet success criteria - the date of first observation of IGA success + 1. The duration of IGA success for subjects who end treatment in IGA success will be censored at the last disease assessment date. Only the first duration of IGA success will be analyzed.

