- **Duration of IGA of 0** = the date of first observation of IGA > 0 - the date of first observation of IGA of 0 and stop treatment. The duration of IGA of 0 for subjects who end treatment in IGA success will be censored at the last disease assessment date. This is for subjects who achieve IGA of 0 and stop the treatment. Subjects who achieve IGA of 0 but never stop treatment will be excluded from the analysis. For subjects who achieve IGA of 0 but stop the treatment later, the duration starts from the date of stop treatment. Only the first IGA of 0 duration will be analyzed.
- **Duration of IGA of 0 or 1** = the date of first observation of IGA > 1-the date of first observation of IGA of 0 or 1 + 1. The duration of IGA of 0 or 1 for subjects who end treatment in IGA of 0 or 1 will be censored at the last disease assessment date. Only the first IGA of 0 or 1 duration will be analyzed.
- **Disease recurrence** = the date of first observation of IGA of 2 or above after achieving IGA of 0 and stop treatment - the date of first observation of IGA of 0 + 1. Only the first disease recurrence will be analyzed.
- **Treatment-free interval** = the date of re-starting study drug due to IGA score above 0 - the date of stop treatment due to attainment of score of IGA of 0 +1, among subjects who achieve a “completely clear” IGA and stop treatment to all lesions. If subjects never re-start study drug after stopping treatment, the treatment-free interval is censored at the end of study date. Only the first treatment-free interval will be analyzed.
- **Weight of IP (g)** = dispensed can weight – returned can weight.
- **BMI (kg/m²)** = (weight in kg)/[(height in cm/100)²]. Day 1 height will be used for BMI derivation upto Week 24. For visits including week 24 through week 36, week 24 height

will be used to derive BMI. Week 52 BMI is derived using the height and weight collected at the same visit. This derivation is applied since height is not collected at all visits.

- **BMI Categories:**

- Underweight: $BMI < 18.5$
- Normal: $18.5 \leq BMI \leq 24.9$
- Overweight: $25.0 \leq BMI \leq 29.9$
- Obese: $BMI \geq 30.0$

- **WI-NRS 4-point reduction** = achievement of a 4-point reduction in WI-NRS pruritus score post-baseline compared to baseline, calculated only for subjects with a pruritus score of ≥ 4 at baseline.
- **Itch-free state** = achievement of in WI-NRS of 0 or 1.

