9.9. Pigmentation Assessment

The hypopigmentation and hyperpigmentation are scored on a 0-3 scale where 0 = none, 1 = mild, 2 = moderate and 3 = severe. A shift table summarizing each category and study visit will be summarized for subjects belonging to Cohort 2 Group 4 for OLE baseline. This summary is repeated for race subgroups as well (white, black, vs others).

10. Changes from Planned Analysis

Per the sponsor request, the following changes have made to the SAP:

- The 2-grade improvement in IGA from Baseline as observed over time endpoint has been removed.
- TEAE by PT, TESAE by SOC, PT table summaries have been added.
- Shift in pigmentation assessment summary for Cohort 2 Group 4 is added.
- Subgroup analysis tables for TEAE by severity have been added.
- The Durations of IGA Success, Duration of IGA 0/1 and other similar duration variables have been updated to be defined from first instance of the event to first subsequent instance of loss of the event, rather than the time from the first instance of the event to the last subsequent instance of the event.

11. Other Planned Analysis

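### After the SAP moved the end of an IGA-success episode to the first loss, it kept the protocol's censoring sentence, so subjects who lose and regain success fall under two conflicting rules

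*SAP*

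**What the plan says.** Protocol 4.2.2 runs the duration from the first success to the last time the success criteria are met, and adds: "The duration of IGA Success for subjects who end treatment in IGA Success will be censored at the last disease assessment date".

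The SAP changes the end point. Section 10 declares that the duration variables are now "defined from first instance of the event to first subsequent instance of loss of the event". SAP 6.1.7 gives the formula: "The date of first observation where IGA does not meet success criteria - the date of first observation of IGA success + 1". SAP 8.2.1 likewise ends the episode when the subject's "disease response does not meet the criteria for IGA Success".

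The censoring sentence stays in SAP 2.2.1.2, 6.1.7 and 8.2.1: "The duration of IGA success for subjects who end treatment in IGA success will be censored at the last disease assessment date". Section 10 does not mention censoring. The parallel rule for IGA 0/1 in SAP 6.1.7 reads the same way: durations "for subjects who end treatment in IGA of 0 or 1 will be censored at the last disease assessment date".

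Three further provisions bear on the point:

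- SAP 8.2.1 limits the analysis to the first episode and describes discontinuers without relapse as censored.
- SAP 8.2.1 censors a subject with no IGA after first success at the end-of-study date.
- The summary is a Kaplan-Meier median in days: "The median time (number of days) for IGA success will be analyzed using the Kaplan–Meier method".

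Scheduled IGAs fall at Weeks 4, 12, 24, 36 and 52, and the phone visits include none. When disease returns, Protocol 6.5 allows an unscheduled visit with an IGA, "although an unscheduled visit is not required as subjects only need to call the site".

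**The concern.** Censoring everyone who ends in success suited the protocol's definition, because for such a subject the last time in success had not yet been seen to pass. It does not suit a first-loss event. The sentence looks at status at the end of treatment, whereas the event depends on what happened after the first success. A subject who relapsed and recovered satisfies both.

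The design makes that path plausible: treatment stops when the investigator confirms clearance and restarts when disease returns. If the sentence is programmed as written, observed losses become late censorings, and that can only raise the curve. This is a named secondary endpoint, repeated by group and from two baselines, and two careful programmers could produce different curves from the same data.

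Two related matters affect the same estimate. Censoring at the end-of-study date credits success time that nobody observed. The SAP also does not say how losses are dated between widely spaced visits.

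**Working it through.** The documents give no median, rate or event count for this endpoint, so there is no figure to reproduce.

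**1. One subject under both rules.** Visit days from the schedule are 29, 85, 169, 253 and 365. Take success on Day 29, loss on Day 85, and success on Days 169, 253 and 365.

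- Reading A, event at first loss: 85 − 29 + 1 = 57 days, event.
- Reading B, literal censoring sentence: 365 − 29 + 1 = 337 days, censored.

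**2. Size under one set of assumptions.** Assume success at Week 4, exponential loss with median 24 weeks (168 days), exponential regain with median 8 or 16 weeks (56 or 112 days), no dropout and scheduled IGAs only. With l = ln2/168, r = ln2/56 or ln2/112, and s = l + r:

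- The chance of being in success t days after a success is p(t) = r/s + (l/s)·exp(−s·t).
- Reading A retention is the product of p over the visit gaps (56, 84, 84, 112 days).
- Reading B retention is 1 minus the summed probability of a first loss by that visit in subjects who are not in success at Week 52. At Week 52 this reduces to p(336).

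| | Regain 8 wk | Regain 16 wk |
|---|---|---|
| p(56), p(84), p(112) | 0.849, 0.813, 0.789 | 0.825, 0.768, 0.726 |
| A, Week 24 | 0.849 × 0.813 = 69% | 0.825 × 0.768 = 63% |
| B, Week 24 | 92% | 83% |
| A, Week 52 | 44% | 35% |
| B, Week 52 = p(336) | 75% | 61% |
| Subjects with an observed loss | 56% | 65% |
| Of those, ending in success | (0.751 − 0.442)/0.558 = 55% | (0.613 − 0.353)/0.647 = 40% |

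**3. A wider range.** A separate simulation used 6,000 subjects per scenario, mean onset 40 days, mean loss 90, 180 or 270 days, and mean regain 30, 60 or 120 days.

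- Reading B removes 34% to 66% of first-loss events and raises Day-180 retention by 15 to 31 points.
- In the middle case (loss 180, regain 60), retention is 66% under A and 90% under B. The median is 281 days under A and not reached under B.
- With regain effectively switched off, the two readings agree.

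**4. The visit grid.** The gaps are 56, 84, 84 and 112 days, that is 8, 12, 12 and 16 weeks. With the +1 convention, on-schedule event times can only be 57, 85, 113, 141, 169, 197, 225, 281 or 337 days. The same simulation without regain gives:

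| Mean loss (days) | Kaplan-Meier median | True median from first-success visit | True median from onset |
|---|---|---|---|
| 90 | 85 | 64 | 89 |
| 180 | 169 | 129 | 154 |
| 270 | 225 | 187 | 214 |

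Measured from the first-success visit, the median is 3 to 6 weeks too long (21, 40 and 38 days). Measured from true onset, the differences are −4, +15 and +11 days, because onset is also seen late.

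**5. End-of-study date.** Suppose first success is on Day 253, there is no later IGA, and the study ends on Day 365. SAP 8.2.1 credits 365 − 253 + 1 = 113 days, whereas the last IGA supports 253 − 253 + 1 = 1 day. This subject also ends in success, so the last-assessment rule applies as well and gives a different date.

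**6. Sibling endpoints.**

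- For duration of IGA 0 (SAP 6.1.7), the event is any IGA above 0, but censoring applies to those who end treatment in IGA success. A subject who moves from 0 to 1 can meet both without regaining anything.
- For disease recurrence (SAP 8.2.1), a subject with another IGA after reaching 0 is censored at the last assessment, with no condition that recurrence is absent.

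**The case against.** A reader might infer that the censoring sentence overrides the first-loss event. The documents do not support that. No precedence is given, and four things point to the event: the formula in SAP 6.1.7, the restriction to the first episode, the link between censoring and absence of relapse, and the change declared in Section 10. A time that runs through a loss into a second success is hardly a first episode. This stands, and it makes the event the better reading. It does not close the gap, because the no-relapse wording covers discontinuers and not completers, and the censoring sentence carries no such condition in any of its three locations.

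A reader might also infer that durability is overstated as planned. That holds only if the less favoured reading is programmed and some subjects regain success. The rates above are assumptions. Stopping applies at IGA 0 while success includes IGA 1, so a restart need not mean that success was lost.

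A third tempting inference is that visit dating biases the median upwards in general. It does not: late-observed onset offsets much of it, and the excess depends on where the true median falls relative to the grid. Nor are losses necessarily dated only at scheduled visits, since unscheduled and early-termination IGAs exist. SAP 6.1.4 admits them only in place of a missing scheduled value, SAP 8.2.1 includes unscheduled ones for the any-time summaries, and nothing is said for durations.

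Finally, success by visit with confidence intervals is already planned, and Protocol 7.4.4 already calls for the rate remaining in success over time. The study is descriptive, so no error rate is affected.

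**Conclusion.** The point holds as a conflict between two stated rules. For subjects who lose and regain success, the SAP gives both an event and a censoring, without saying which prevails. The surrounding text favours the event. If the sentence were applied literally, the curve could only move up. Under the assumed rates, Day-180 retention rises by 15 to 31 points and 34% to 66% of events disappear; without regain the effect is essentially nil. The actual size cannot be known from the documents.

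The end-of-study censoring rule is a separate, smaller defect in the same direction. The visit spacing makes the median coarse but does not establish a general upward bias. The change should be made before analysis; because this is a descriptive secondary endpoint, nothing beyond its reporting is at stake.

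**What to change.** 1. In SAP 2.2.1.2, 6.1.7 and 8.2.1, replace the censoring sentence with wording such as: *A subject with any observed loss after first success has an event at that first loss, whatever the later grade. Only subjects with no observed loss are censored, at their last IGA.* This also replaces the end-of-study-date rule. Align the censoring for IGA 0/1, IGA 0 and disease recurrence in the same way.
2. State whether unscheduled IGAs count in the duration analyses, and how this fits with SAP 6.1.4.
3. Beside the planned Kaplan-Meier analysis, add an interval-censored sensitivity estimate (Turnbull, for example PROC ICLIFETEST), with each loss placed between the last success visit and the first non-success visit. Report the share still in success at scheduled visits alongside the median, not in place of it.

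The cost is a few sentences of SAP text and one extra SAS procedure. Reported durations may come out shorter.

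### The censoring rule for time to disease recurrence in SAP 8.2.1 contradicts its own event definition, and leaves some subjects with no later IGA without any rule

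*SAP*

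**What the plan says.** **Event.** SAP 8.2.1, under Disease recurrence: "Time to disease recurrence is defined as time from first observation of IGA of 0 and stop treatment to first observation of IGA of 2". Grades above 2 count as well, and the grade must be seen once treatment has stopped. SAP 6.1.7 ends the interval at the same point: "the date of first observation of IGA of 2 or above after achieving IGA of 0 and stop treatment".

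**Who is analysed.** "Subjects who achieve IGA of 0 but never stop treatment will be excluded from analysis". In 8.2.1, if a subject stops some days after reaching IGA 0, the clock starts at the stop date.

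**Censoring, sentence 1.** "If there is other IGA assessment after achieving IGA of 0, the time to disease recurrence will be censored at the last disease assessment date".

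**Censoring, sentence 2.** "If there is no IGA assessment after the first observation of IGA success, the duration will be censored at the end of study date".

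**Method.** "The analysis of time to disease recurrence will be in the similar fashion as the analysis of duration of IGA success". In the paragraph on duration of IGA success, the corresponding text is: "Subjects who discontinue study without relapse will be considered censored in the Kaplan–Meier analyses".

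SAP 6.1.7 gives censoring rules for duration of IGA success, duration of IGA of 0, duration of IGA of 0 or 1, and treatment-free interval. It gives none for disease recurrence.

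**The concern.** A time-to-event analysis needs one unambiguous status, event or censored, for each subject. Here the event definition and sentence 1 give opposite answers for the same subjects. Sentence 1 applies whenever another IGA exists after IGA 0, and does not ask what that IGA showed. Every recurrence is itself another IGA after IGA 0.

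The neighbouring variables do depend on outcome. Duration of IGA success is censored for those who end treatment still in success, and treatment-free interval for those who never restart. Only the recurrence rule lacks such a condition, which looks like a drafting omission.

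Sentence 2 has a different fault: it refers to IGA success, which is not the state from which recurrence is measured. Left as they are, the two sentences have to be interpreted at programming, and two programmers could produce different Kaplan-Meier curves from the same data.

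**Working it through.** The documents give no event count, rate or median for this analysis, so there is no figure to reproduce. The check is one of logic.

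**Step 1. Inputs and assumptions.** IGA grades are 0 to 4, and the clinic visits are at Weeks 4, 12, 24, 36 and 52 (protocol 1.3). IGA success is IGA 0 or 1 plus a 2-grade improvement, with subjects at IGA 0 or 1 at baseline excluded (SAP 6.1.7). Assumptions: open-label baseline IGA may be 0 to 4; dropout is monotone; a 2-grade improvement means at least two grades; treatment stops on the day of the first IGA 0. Every path that reaches IGA 0 was enumerated. The counts are unweighted and say nothing about how often a path would occur.

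**Step 2. Paths reaching IGA 0.** With L visits attended there are 5^L − 4^L such paths: 1 + 9 + 61 + 369 + 2,101 = 2,541. Over five baseline grades: 2,541 × 5 = 12,705.

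**Step 3. Sentence 1.** Paths whose first IGA 0 is the last assessment number 4^(L−1): 1 + 4 + 16 + 64 + 256 = 341 per baseline grade, or 1,705 in all. The other 12,705 − 1,705 = 11,000 have a later IGA and meet sentence 1.

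**Step 4. Recurrences.** Among those 11,000, paths whose later grades are all 0 or 1 number 30 + 56 + 96 + 128 = 310 per baseline grade (first IGA 0 at visit 1, 2, 3 or 4), or 1,550. The remaining 11,000 − 1,550 = 9,450 contain an IGA of 2 or above. All 9,450 meet sentence 1, as they must.

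**Step 5. Sentence 2.** This applies among the 1,705 paths with no later IGA.

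| Baseline IGA | Paths, no later IGA | Meet sentence 2 | No rule |
|---|---|---|---|
| 0 | 341 | 0 (success not defined) | 341 |
| 1 | 341 | 0 (success not defined) | 341 |
| 2 | 341 | 341 (success only at IGA 0) | 0 |
| 3 | 341 | 121 (no earlier IGA 1) | 220 |
| 4 | 341 | 121 (no earlier IGA 1) | 220 |
| Total | 1,705 | 583 | 1,122 |

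Here 121 = 1 + 3 + 9 + 27 + 81. A concrete case: baseline IGA 3, IGA 1 at Week 4 (success), IGA 0 at Week 12, nothing after. There is no IGA after IGA 0, so sentence 1 does not apply. There is an IGA after the first success, so sentence 2 does not apply either. None of the 1,122 paths can contain a recurrence, because none has a later IGA.

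**Step 6. What the ambiguity does to a curve.** In an invented set of ten subjects with five recurrences, if sentence 1 overrides the event definition there are 0 events and the estimate stays at 1.000. With the event first, the recurrences fall at days 57, 85, 141, 169 and 225, with 8, 7, 6, 5 and 3 at risk: 7/8 × 6/7 × 5/6 × 4/5 × 2/3 = 0.333. This only illustrates the gap between the two readings.

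**Step 7. Anchor of sentence 1.** It looks for assessments after IGA 0, while 8.2.1 can start the clock later, at the stop date. A subject whose only other IGA falls between the two would be censored before the clock starts. The stop date is the consistent anchor for both sentences.

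**The case against.** The strongest reply is that no sensible programmer would let sentence 1 cancel the event. The event is defined explicitly in both 8.2.1 and 6.1.7, and 6.1.7 adds that only the first recurrence counts. Censoring ordinarily applies to subjects without the event. The paragraph closes by carrying over the method for duration of IGA success, where discontinuers are censored if they have not relapsed. On this view the two sentences only say where to censor subjects who have not recurred.

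Much of that stands. A reader might infer from sentence 1 that the plan yields no events and a curve fixed at 100% recurrence-free. The documents do not support that as a finding: it follows only if sentence 1 outranks the event definition. The SAP states no such priority, and the cross-reference points the other way. A reader might also infer that the two sentences between them cover every subject. They do not, as Step 5 shows.

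The reply does not remove the inconsistency. The carried-over sentence covers only subjects who discontinue, and the paragraph does not define relapse for this variable. A general cross-reference does not clearly override a sentence written for this variable. Nor does applying the event first help subjects who meet neither sentence.

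The importance is limited. Disease recurrence is not among the endpoints in protocol 4.2 or SAP 2.2, and SAP 6.1.2 plans no inferential analysis. It is also not the only measure of how long clearance lasts off drug: duration of IGA of 0 and treatment-free interval are both analysed in subjects who clear and stop.

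**Conclusion.** The point holds as an internally inconsistent and incomplete censoring rule. Taken literally, sentence 1 censors every subject who has the event the same paragraph defines. With the event applied first the rule works for subjects who recur, but the SAP does not say to do so, and 6.1.7 supplies no rule that would settle it. Separately, sentence 2 is keyed to the wrong state, so some subjects with no later IGA have no censoring rule: 1,122 of the 1,705 enumerated paths of that kind, under the Step 1 assumptions. The size in the trial cannot be stated, because the documents do not give the number of subjects expected to clear and stop.

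The consequence is confined to one descriptive Kaplan-Meier analysis. The primary safety endpoints and the listed efficacy endpoints are unaffected. Because the text contradicts itself and costs little to correct, it should be corrected before the derivation is programmed.

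**What to change.** Put the same three rules in SAP 8.2.1 and SAP 6.1.7:

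1. A subject with an IGA of 2 or above after the treatment stop date has an event on the date of the first such IGA.
2. A subject with at least one IGA after the stop date, all below 2, is censored at the last of those assessments.
3. A subject with no IGA after the stop date is censored at the end of study date, as sentence 2 already provides. The trigger becomes the stop date in place of first IGA success.

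Adding only a no-recurrence condition to sentence 1 would not be enough, because sentence 2 would keep its wrong anchor. The cost is a few sentences in two places and a small change to one derivation, with no new data or assessments.
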